Clinical investigation plan

C20-688 (EX-MKTG-120)

Using personal face masks with spectacles
versus contact lenses

A clinical evaluation for CooperVision Inc.

Study Leader
[name]

Principal Investigator
[name]

September 2020

Contents

Section 1. Overview	5
1.1 Background	5
1.2 Personnel	5
1.3 Study objectives	5
1.4 Study design	5
1.5 Statistical considerations	6
1.6 Risk analysis	6
Section 2. Resources	8
2.1 Subject selection	8
2.2 Subject discontinuation	9
2.3 Safety parameters, adverse events and concurrent illnesses	10
2.4 Study termination	10
2.5 Protocol deviations	10
2.6 Study resources	11
2.7 Study control	12
2.8 Documentation	12
2.9 Data collection and analysis	12
2.10 Study completion	12
2.11 Confidentiality	12
2.12 Study monitoring	12
2.13 Clinical trial registration	13
Section 3. Subject management	14
3.1 Visit scheduling	14
3.2 Visit conduct	14
3.3 Monitoring subject compliance	20
3.4 Missing, unused and spurious data	20
Section 4. Study co-ordination	21
4.1 Document processing	21
4.2 Disclosure	21
4.3 Personnel	21

Study summary

The aim of this study is to explore (a) satisfaction with vision correction and (b) ease of use of personal face masks (PFM) in a group of spectacle wearers and a group of newly-fitted contact lens wearers. This will be a two-arm, parallel-group, randomised study. Up to 35 single vision spectacle wearers will be recruited to participate in the study. Subjects will be randomised to either continue to wear their spectacles or to be fitted with the study daily disposable (DD) contact lens (clariti 1 day, CooperVision Inc.), for a period of two weeks.

[REDACTED]

[REDACTED]

A study summary is shown in Table 1.

V st	Procedures
Inta v st	
Information and consent forms signed
 
Medical and ocular histories
 
[REDACTED] visual acuity
 
Subjective scores and questionnaires
 
[REDACTED]
 
Confirmation of eligibility
 
Randomisation to treatment type
 
Vision, subjective scores, [REDACTED] (contact lens group only)
 
Contact lens application/removal/education session (contact lens group only)
 
[REDACTED]

2 week v st	
Medical and ocular histories
 
Subjective scores and questionnaires
 
Visual acuity
 
[REDACTED]
 
Study exit and payment issued

Table 1: Study summary.

Section 1. Overview

1.1 Background

The transmission of COVID-19 is thought to occur mainly through small droplets released after coughing, sneezing and through contact with contaminated surfaces. Use of personal face masks (PFM) is considered to be one of the most important strategies for protecting the wearer from this and other infectious diseases.

Although PFM is aimed to protect the user, it has the potential to negatively impact upon day to day tasks as well as individual work performance. Face protection such as masks, goggles and face shields are often worn for hours at a time and anecdotal evidence suggests that use of prescribed spectacles in combination with PFM can be difficult. One of the most common problems encountered is fogging of spectacles whilst wearing a face mask. This can result in significantly impaired vision which may interfere with the performance of daily activities. Furthermore, the use of spectacles with masks and other forms of PFM is physically uncomfortable. One way to potentially overcome these issues is to fit contact lenses.

1.3 Study objectives

The aim of this study is to explore (a) satisfaction with vision correction and (b) ease of use of PFM in a group of spectacle wearers who will be randomised to continue wearing spectacles or be fitted with daily disposable contact lenses.

1.4 Study design

This will be a two-arm parallel-group, randomised study. Thirty-five single vision spectacle wearers will be recruited to participate in the study. Subjects will be randomised to either continue to use their spectacles or to be fitted with the study daily disposable (DD) contact lens (clariti 1 day, CooperVision Inc.). Subjects will attend the clinic for two visits.

At the initial visit, subjects will sign the consent form and be screened according to the inclusion/exclusion criteria. [REDACTED]

[REDACTED]

[REDACTED]. Subjects will be randomised to either continue to wear their spectacles or to the study contact lens for two weeks. Subjects randomised to the contact lens group will be fitted with the study DD contact lens and will receive a training/education session on contact lens application and removal. All subjects will be supplied with disposable surgical masks (Type I or II) and asked to wear them for the majority of the time that they need to wear PFM and for at least one hour per day. After two weeks, subjects will return to the clinic for a final visit, where the clinical assessments will be repeated.

1.5 Statistical considerations

The principal hypothesis to be tested in this work is that subjective scores for the spectacle group and contact lens group will be the same.

Visual acuity, [REDACTED] and subjective responses will generate data that are likely to be continuous and normally distributed. As such, these will be compared using linear regression models or other parametric methods. [REDACTED]

[REDACTED] Deviations from this statistical plan will be discussed in the final report. Deviations may be necessary due to differences between the actual data distribution compared with the anticipated data distribution.

1.5.1 [REDACTED]

[REDACTED]
[REDACTED]
[REDACTED]
[REDACTED]
[REDACTED]

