2.1 Subject selection

In this work, up to 35 subjects will be consented with the aim of 15 subjects completing the study in each group.

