3.2.2 Initial visit

Subjects should attend this visit wearing (or having brought along) their habitual spectacles.

They will then be required to sign an informed consent form prior to enrolment [REDACTED]

[REDACTED]. A copy of the signed form will be issued to the subject. When the subject has signed the consent form, they are considered to be enrolled on the study.

Subjects will be instructed on the following:

1. Lens handling, application and removal, where necessary.
2. Specific study instructions, such as the importance of not using any other contact lens products.
3. General contact lens information such as the management of red eyes.

The following procedures will be performed (any ocular measurement procedures outlined below will be carried out on each eye):

1. Details of the ocular history.
2. Details of general health and medications.
3. Details of PFM use (type of PFM, hours per day, days per week).
4. The BVD of the subject's spectacles by asking the subject to position the spectacles on their own face (if not already being worn).
5. Focimetry will be carried out on the subject's spectacles to ascertain the prescription of the lenses.
6. The investigator will perform refraction and distance and near monocular logMAR visual acuity (both high and low contrast), in accordance with the current Eurolens Research Standard Operating Procedure 'The set up, measurement of visual acuity and procedures for carrying out an over refraction using the Eurolens computerised logMAR VA chart'.
7. The investigator will assess whether or not the subject's single vision spectacles have a mean sphere equivalent within $\pm 0.50\text{D}$ of that found for the refraction after having taken effectivity into account.
8. [REDACTED]
9. Facemask usability questionnaire [5-point scale from 1 (very unsatisfactory) to 5 (very satisfactory)] will be completed [REDACTED]
 - a. Breathability
 - b. Heat
 - c. Tightness
 - d. Ease in talking
 - e. Comfort on ear lobes
 - f. Overall comfort

11. Questions about using the mask during day-to-day activities/tasks [REDACTED]

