3.2.3 Follow-up visit

*For the contact lens group, subjects should attend wearing the study lenses which should have been *in situ* for at least two hours. Subjects who attend without lenses *in situ* for at least two hours will usually be rescheduled. For the spectacle group, subjects should attend wearing their spectacles. Spectacles should have been worn for a minimum of two hours on the day of the visit.*

The following procedures will be performed:

1. Any medical or ocular issues since the last visit.
2. Spectacle or contact lens wearing times since the previous visit (hours per day, days per week and comfortable hours per day).
3. Spectacle or contact lens wearing time on study visit day.
4. Surgical mask wearing times since the previous visit (hours per day, days per week and comfortable hours per day).
5. [REDACTED]
6. Facemask usability questionnaire will be completed [REDACTED]
7. [REDACTED]
- [REDACTED]
- [REDACTED]
- [REDACTED]
- [REDACTED]

[REDACTED]

[REDACTED]

[REDACTED]

[REDACTED]

[REDACTED]

8. Questions about using the mask during day-to-day activities/tasks [REDACTED]

[REDACTED]

9. [REDACTED]

[REDACTED]

[REDACTED]

[REDACTED]

[REDACTED]

[REDACTED]

[REDACTED]

[REDACTED]

[REDACTED]

11. For spectacle wearers, monocular logMAR visual acuity (high contrast) will be recorded. Proceed to step 15.

12. For contact lens wearers, monocular logMAR visual acuity (high contrast) will be recorded before performing an over-refraction, and then monocular logMAR visual acuity (high and low contrast) will be carried out [REDACTED] as described in section 3.2.2.

13. [REDACTED]

[REDACTED]

[REDACTED]

[REDACTED]

15. The subject will be issued with their payment and discharged.

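### Does leaving the two-eye analysis unit and the compared lens reading unstated make the visual acuity comparison wrong?

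*Combined protocol and SAP*

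**What the plan says.** Section 1.5 groups acuity with the subjective responses: "Visual acuity, [REDACTED] and subjective responses will generate data that are likely to be continuous and normally distributed". It gives one method for both: "As such, these will be compared using linear regression models or other parametric methods". The sentences that follow, and the whole of 1.5.1, are redacted. The principal hypothesis in the same section does not involve acuity. It begins "The principal hypothesis to be tested in this work is that subjective scores for the spectacle group and contact lens group" and goes on to posit no difference.

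Section 3.2.2 states that "any ocular measurement procedures outlined below will be carried out on each eye", so each subject supplies two values for every acuity reading. At baseline, step 6 lists high- and low-contrast acuity for everyone.

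At follow-up (3.2.3) the arms diverge. Step 11 reads "For spectacle wearers, monocular logMAR visual acuity (high contrast) will be recorded. Proceed to step 15", and step 15 is payment and discharge. Step 12 gives lens wearers a high-contrast reading before over-refraction, after which "monocular logMAR visual acuity (high and low contrast) will be carried out", with a reference back to 3.2.2, where the over-refraction is in place. The overview in 1.4 describes the final visit as one "where the clinical assessments will be repeated".

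On size, section 2.1 says "up to 35 subjects will be consented with the aim of 15 subjects completing the study in each group".

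**The concern.** Two features look wrong on a first reading.

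The first is the unit of analysis. Two eyes of one person are correlated, and treatment is assigned to the person. A regression with one row per eye and no subject term would count 30 people as 60 independent observations. Its standard errors would be too small, and it would declare acuity differences too often.

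The second is comparability. Lens wearers have two high-contrast readings at follow-up and spectacle wearers have one. Comparing the over-refracted lens reading with acuity in habitual spectacles would set vision with residual error removed against vision as the subject presents. Exclusion criterion 13 allows those spectacles to be up to 0.50 D from the refraction. Such a comparison would flatter the sponsor's lens. Low-contrast acuity has no visible spectacle counterpart at follow-up, which does not fit the overview in 1.4.

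**Working it through.** **Planned size.** The target is 15 completers per arm, so 30 subjects and 60 eyes (2.1). No alpha, power, effect size or standard deviation is visible, so the 15 per arm can be neither reproduced nor refuted.

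**Effect of treating eyes as independent.** The assumptions, none of them in the visible text, are a two-sided alpha of 0.05, the same correlation ρ between the eyes of every subject, and ρ from 0.5 to 0.9 as the main range. With two eyes per subject and treatment varying only between subjects:

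- design effect = 1 + ρ
- naive SE / true SE = 1/√(1 + ρ)
- actual type I error ≈ 2 × [1 − Φ(1.96/√(1 + ρ))]

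At ρ = 0.5, √1.5 = 1.225. The naive SE is 1/1.225 = 0.82 of the true one (18% too small), and the error rate is 2 × [1 − Φ(1.600)] = 0.110. At ρ = 0.9, √1.9 = 1.378. The ratio is 0.73 (27% too small), and the error rate is 2 × [1 − Φ(1.422)] = 0.155.

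A simulation of 200,000 trials per setting, with 15 subjects per arm and two eyes each, gave:

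| ρ | naive SE / true SE | type I error, normal approximation | type I error, eyes as rows (simulated) | type I error, subject means (simulated) |
|---|---|---|---|---|
| 0.3 | 0.88 | 0.086 | 0.086 | 0.050 |
| 0.5 | 0.82 | 0.110 | 0.111 | 0.049 |
| 0.7 | 0.77 | 0.133 | 0.138 | 0.051 |
| 0.8 | 0.75 | 0.144 | 0.149 | 0.051 |
| 0.9 | 0.73 | 0.155 | 0.163 | 0.050 |

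Thirty eyes per arm would carry the information of 30/1.5 = 20 independent eyes at ρ = 0.5, and 30/1.9 = 15.8 at ρ = 0.9. The arithmetic of the concern is therefore sound, provided eyes are entered as independent rows.

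**Does the plan specify that analysis?** The visible wording of 1.5 names neither the eye nor the subject as the unit, and it does not restrict the regression to independent errors. A regression on the mean of the two eyes, a mixed model with a subject effect, and regression with clustered standard errors all fall within it. A rule on paired eyes may also sit in the redacted text.

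**Are the follow-up readings comparable?**

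| Follow-up reading (3.2.3) | Spectacle arm | Lens arm |
|---|---|---|
| High contrast, with the correction as worn | step 11 | step 12, first reading |
| High contrast, after over-refraction | not listed | step 12, second reading |
| Low contrast, after over-refraction | not listed | step 12, second reading |

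The first row is like-for-like and available in both arms. The other two rows are extra readings in one arm, and no visible sentence plans a between-arm test on them.

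**The case for a change.** The best argument for a change is that the plan leaves a choice open until the data are in. Lens wearers have two high-contrast values, the text does not say which is compared, and one choice favours the sponsor's product. The unit of analysis is open in the same way, and the penalty for getting it wrong is not trivial: even at ρ = 0.3 the error rate would be about 8.6%. A few sentences would close both gaps at no cost to subjects. Redaction does not fully answer the procedural point, because steps 11 and 12 are largely legible and the jump to step 15 bypasses whatever steps 13 and 14 contain.

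Some of this stands. The visible text does not name the unit or the compared reading, and 1.4 is looser than 3.2.3 on low-contrast acuity. But none of it shows that the plan, followed as written, gives a wrong result. Only one reading is taken under the same condition in both arms, so the natural comparison is clear. The line in 1.4 is a design overview; 3.2.3 is the operative schedule, and the mismatch alters no analysis. The visible questionnaire items are answered once per subject, so two-eye correlation does not reach them.

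**Conclusion.** No change to the plan is needed. The inflation to about 11% to 16%, with standard errors 18% to 27% too small, is conditional on three things: eyes analysed as independent, a between-eye correlation of 0.5 to 0.9, and a two-sided 5% test. The documents state none of these. With one value per subject, which the stated methods allow, the simulated error rate stays at 4.9% to 5.1%. The matched acuity comparison is already collected through steps 11 and 12 of 3.2.3, and the lens-only readings do no harm unless someone sets them against spectacles, which no visible text proposes. Any residual effect is confined to acuity and does not touch the principal hypothesis on subjective scores. This is ordinary missing detail in a small exploratory study, with part of the statistical section redacted, and a competent analyst would settle it correctly.

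### Does calling 5-point mask ratings continuous and normal, with no visible named score, undermine the test of the principal hypothesis?

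*Combined protocol and SAP*

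**What the plan says.** Section 1.5 states one hypothesis: "The principal hypothesis to be tested in this work is that subjective scores for the spectacle group and contact lens group will be the same". It then says that "subjective responses will generate data that are likely to be continuous and normally distributed", and on that basis plans linear regression or other parametric methods. It adds that departures from the plan will be discussed in the final report and that "Deviations may be necessary due to differences between the actual data distribution compared with the anticipated data distribution".

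Section 1.3 gives two aims without ranking them: to "explore (a) satisfaction with vision correction and (b) ease of use of PFM".

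The mask questionnaire in section 3.2.2, step 9, uses a "5-point scale from 1 (very unsatisfactory) to 5 (very satisfactory") and lists six items: breathability, heat, tightness, ease in talking, ear-lobe comfort and overall comfort. Section 3.2.3, step 6, repeats it at two weeks: "Facemask usability questionnaire will be completed". No total or mean score is defined in the visible text.

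Table 1 of the Study summary lists "Subjective scores and questionnaires" at both visits. For the contact lens group after randomisation it lists subjective scores again, with no visible mention of questionnaires.

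Section 2.1 aims for 15 completers in each group.

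**The concern.** A rating that can take only five values is neither continuous nor normal, and 15 subjects per group is few enough that one would not lean on large-sample theory without checking. If the regression lost control of its error rate on such data, the principal test would be unreliable.

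The second worry is larger. The hypothesis refers to scores in the plural, there are two aims, and at least six items are visible. If the score, the use of baseline and the trigger for changing method were all left open until the data were seen, the favourable analysis could be picked afterwards and the nominal 5% would no longer hold. The choice of score would also decide how much power 15 per group gives.

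**Working it through.** **Inputs.** From the documents: 15 completers per group (2.1), six items scored 1 to 5 (3.2.2), questionnaire at both visits (3.2.2, 3.2.3). Assumed, because not visible: two-sided 5% level, shape of the ratings, correlation between items, correlation with baseline. The plan shows no power calculation, so there is no figure of its own to reproduce on this point.

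**Step 1: does linear regression hold its level on one 5-point item?** Regression on group alone is the two-sample t test, t = (m1 − m2) / √[(s1² + s2²)/15] on 28 degrees of freedom. With 200,000 simulated null trials per shape (simulation error about √(0.05 × 0.95/200,000) = 0.05 points), and 20,000 trials for regression adjusted for baseline (latent correlation 0.5; error about 0.15 points):

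| Probabilities of ratings 1 to 5 | t test | Adjusted for baseline |
|---|---|---|
| 0.10, 0.20, 0.40, 0.20, 0.10 | 5.05% | 5.05% |
| 0.03, 0.07, 0.20, 0.40, 0.30 | 5.00% | 5.15% |
| 0.01, 0.02, 0.07, 0.20, 0.70 | 4.51% | 4.55% |
| 0.20 each | 5.14% | 5.09% |
| 0.35, 0.10, 0.10, 0.10, 0.35 | 5.17% | 4.92% |

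The worst departure is slightly conservative, with 70% of subjects at the top score.

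**Step 2: does freedom to switch method matter?** Taking the better of the t test and the Wilcoxon test on one item gives 5.5% to 5.9% under the null, over three assumed rating shapes with both correlations at 0.5. That is less than one percentage point above nominal.

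**Step 3: what would an unnamed score cost?** If any of six independent items could count, the chance of at least one false positive is 1 − 0.95⁶ = 26.5%. With simulated item correlations of 0.3, 0.5 and 0.7 it is 24.3%, 22.0% and 18.2%. The mean of the six items, fixed in advance, stays at 4.9% to 5.1%. A smaller menu (overall comfort or the six-item mean, each with or without baseline) gives 9.6% to 14.0% for the best of four, over 27 settings of 20,000 trials (three rating shapes, item correlation 0.3 to 0.7, baseline correlation 0.3 to 0.7). These are costs of an open choice; they do not show that the choice is open.

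**Step 4: is there one score that should be written in?** Power for a shift of 0.8 latent SD in all six items, ratings split 5/10/20/35/30%, both correlations 0.5:

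| | Unadjusted | Adjusted for baseline |
|---|---|---|
| Single item | 46.8% | 53.5% |
| Six-item mean | 73.8% | 82.2% |

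If only one item shifts, the adjusted mean has 5.6% to 9.2% power and the affected item 42.8% to 60.8%. If two shift, the mean has 9.7% to 21.6%. The better score depends on where the effect is expected, and the visible text does not say.

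**Step 5: where would the naming text stand?** In 1.5, blacked-out text directly follows the sentence on parametric methods, and more precedes the sentence on deviations. All of 1.5.1 is blacked out, heading included. Step 8 of 3.2.2 and steps 5, 7 and 9 of 3.2.3 are blacked out, and step 10 is not visible in either section. No visible instrument measures satisfaction with vision correction, so the instrument for the first aim presumably lies in hidden text. Table 1 names scores and questionnaires side by side, so the scores in the hypothesis may be a different measure on a finer scale, for which a continuous description would be reasonable.

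**The case for a change.** The strongest case for a change is that section 1.5 does more than explore: it states a principal hypothesis to be tested. The visible text leaves the score, the covariate and the trigger for a change of method unnamed. Filling that gap would take two or three sentences and no new data, and step 3 shows that an open choice could multiply the error rate between two and five times. If the hidden text already names the score, confirming it costs nothing.

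Much of this stands. For the six mask items the description is literally wrong, and one score fixed beforehand is better than several. What does not follow is a defect in the plan. Text removed from the public copy cannot be counted as absent, and the gap lies where text was removed. The error rates in step 3 and the power contrast in step 4 come from menus that the plan nowhere proposes.

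Baseline adjustment is sensible and did no harm to the error rate, but it too may be in the redacted model text. Its gain is also uncertain. The first questionnaire is step 9, before the study masks are supplied at step 22, so the initial rating may concern another mask. Across the settings examined, the lowest power for the six-item mean rises only from 55.5% to 57.0% with adjustment.

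**Conclusion.** No change to the plan follows. The wording about continuous, normal data is loose for the six visible items but has no practical consequence: planned linear regression on one score rejects in about 4.5% to 5.2% of null trials at 15 per group, and a later switch to a rank test would add less than one percentage point. Section 1.5 already undertakes to discuss deviations in the final report.

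The score for the principal hypothesis may well be named in text that the public copy does not show. The sponsor can usefully check two things in the unredacted 1.5 and 1.5.1: that one score is named, and that the regression uses the initial-visit value where the questionnaire is completed twice. The reason to look is the 18% to 26% chance of a false positive if any of the six mask items could count. No particular composite should be prescribed, because the six-item mean has only about 6% to 9% power when a single item is affected.

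The figures rest on an assumed two-sided 5% level, assumed rating shapes, and assumed correlations of 0.3 to 0.7 (or independence between items). The conclusion on the method is the same for every shape tried.
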